6.2.3 Dose limiting toxicity (DLT)

A dose-limiting toxicity (DLT) is defined as an adverse event or abnormal laboratory value assessed as at least possibly related to study treatment that occurs within the first 6 weeks and meets any of the criteria included in Table 7. National Cancer Institute Common Terminology Criteria for Adverse events (NCI CTCAE) version 4.03 will be used for all grading.

The investigator must notify the Sponsor immediately of any unexpected CTCAE grade ≥ 3 adverse events or laboratory abnormalities. Prior to enrolling patients into a higher dose level, CTCAE grade ≥ 2 adverse events will be reviewed for all patients at the current dose level.

Table 7 Criteria for defining dose-limiting toxicities

Table / Criteria for defining dose mining toxicities					
DLT CRITERIA					
Thrombocytopenia Grade 3 with clinically significant bleeding					
Thrombocytopenia Grade 4					
Neutropenia Grade 4 lasting more than 8 days					
Febrile neutropenia CTCAE Grade ≥ 3					
Diarrhea CTCAE Grade $\geq 3 \geq 72$ hrs., despite the use of anti-diarrhea therapy					
Nausea/ vomiting CTCAE Grade \geq 3 \geq 72 hrs., despite the use of anti-emetic therapy					
• CTCAE Grade 2 pneumonitis if it persists > 7 days despite treatment with corticosteroids.					
• Second episode of grade 2 pneumonitis of any duration					
• Grade 3-4 pneumonitis of any duration					
• CTCAE Grade 3 immune-related toxicities that persist > 14 days with same severity despite treatment with corticosteroids.					
• Immune-related toxicities CTCAE Grade 4 of any duration					
Grade 3-4 infusion reaction					

Protocol/Version No.: 5, Date December 15, 2022

- Other non-hematologic treatment-related toxicity at Grade 3 or higher
- Any AE that leads to permanent discontinuation of siltuximab or spartalizumab
- Death
- 6.2.4 Dose expansion 24 patients will be treated on the dose expansion at the RP2D dose.
- 6.2.5 Duration of therapy: Subjects may withdraw consent at any time for any reason or be dropped from the trial at the discretion of the investigator should any untoward effect occur. In addition, a subject may be withdrawn by the investigator if enrollment into the trial is inappropriate, the trial plan is violated, or for administrative and/or other safety reasons. A subject must be discontinued from the trial for any of the following reasons:
 - The subject or legal representative (such as a parent or legal guardian) withdraws consent.

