The dosing modification requirements are mandatory, however, the AE management guidelines are recommendations and can be modified according to the local practices.

Table 8.0 Mandatory dose modification requirements and recommended clinical management guidelines for potential immune-related diarrhea/colitis

Diarrhea/Colitis (NCI-CTCAE v	1100/	
Grade	Recommended Adverse Event management guidelines	Mandatory Dose Modification requirements
Grade 1 (< 4 bowel actions per day over baseline) mild Grade 2 (4-6 bowel actions per day over baseline) and / or abdominal pain/ blood in stool.	 Diet Hydration Loperamide: initially 4 mg, followed by 2 mg every four hours or after every unformed stool; maximum 16 mg/day. Continue until diarrhea free for 12 hours; Diarrhea > 24h: loperamide 2 mg every two hours; maximum 16 mg/day. Consider adding oral antibiotics. Diarrhea > 48hrs: loperamide 2 mg every two hours; maximum 16 mg/day. Consider other second-line therapies for diarrhea (e.g: (octreotide, oral diphenoxylate) and oral antibiotics If Grade 2 and no improvement in 5 days may require oral steroids If Grade 2 diarrhea persists >1 week consider Gl consultation and endoscopy to 	Continue spartalizumab treatment If diarrhea is Grade 2, despite loperamide at 2 mg every two hours for > 48hrs:

Protocol/Version No.: 5, Date December 15, 2022

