	 If symptoms worsen during steroid reduction, initiate a re-tapering of steroids starting at a higher dose of 80 or 100 mg followed by a more prolonged taper and administer infliximab. If symptoms persist despite the above treatment a surgical consult should be 	
	obtained.	
Grade 4: Life-threatening consequences; urgent intervention indicated	Same as Grade 3	Permanently discontinue spartalizumab

Table 8-1 Mandatory dose modification requirements and recommended clinical management guidelines for potential immune-related liver laboratory alterations

Abnormal liver function tests		
Severity	Recommended Adverse Event management guidelines	Mandatory Dose Modification requirements
Grade 2: AST or ALT > 3x ULN to ≤ 5.0x ULN and/or bilirubin > 1.5x ULN to ≤ 3x ULN (if patient meets criteria for Hy's law refer to section	Monitor hepatic laboratory tests more frequently (every 2-3 days) until returned to baseline values	 Interrupt spartalizumab treatment until recovery to Grade ≤1 or baseline Once recovered restart spartalizumab treatment at the same dose and schedule
6.5)		 Patients with baseline grade 2 AST/ALT value (>3.0-5.0 ULN) may continue spartalizumab treatment

Protocol Study No: Winship4463-18 Product: Siltuximab plus Spartalizumab Protocol/Version No.: 5, Date December 15, 2022

Abnormal liver function tests		
Severity	Recommended Adverse Event management guidelines	Mandatory Dose Modification requirements

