Grade 3 or 4: AST or ALT >5.0xULN and/or bilirubin > 3.0x ULN	 Monitor hepatic laboratory tests more frequently (every 2-3 days) until returned to baseline values. Consider viral serology (i.e. hepatitis A/B/C, CMV, and rule out other potential cause of liver injury such as conmeds or alcohol), consultation with hepatologist and liver biopsy to establish etiology of hepatic injury If after 2-3 days new liver assessment shows worsening of laboratory test consider to initiate treatment with steroids prednisone 1-2 mg/kg/day or IV equivalents. Add prophylactic antibiotics for opportunistic infections as appropriate When symptoms/liver function tests improve to Grade ≤1, taper steroids over at least 4 weeks. If serum transaminase levels or bilirubin do not decrease 48 hours after initiation of systemic steroids, oral mycophenolate mofetil 500 mg every 12 hours may be given as per local treatment guidance. Infliximab is not recommended due to its potential for hepatotoxicity 	 Permanently discontinue spartalizumab Patients with baseline grade 2 AST/ALT value (>3.0-5.0 ULN) will discontinue spartalizumab treatment if value increased to grade 3 with increase >=2x baseline

Table 8-2 Mandatory dose modification requirements and recommended clinical management guidelines for potential immune-related skin events

Rash Events (NCI-CTCAE v4.03)		
Grade	Recommended Adverse Event management guidelines	Mandatory Dose Modification requirements
Grade 1: Rash covering < 10% Body Surface Area (BSA)	 Initiate prophylactic and symptomatic treatment measures. Consider use of topical corticosteroids or urea containing creams in combination with oral antipruritics or moderate strength topical steroid (hydrocortisone 2.5% cream or fluticasone propionate 0.5% cream) 	Continue spartalizumab treatment
Grade 2: 10-30% of BSA	 Reassess after 2 weeks. If tolerable, treat as per Grade 1; If intolerable, initiate systemic steroids (e.g. oral prednisolone 0.5-1mg/kg daily) and consider dose interruption until tolerable or recovery to grade <=1 or baseline; once recovered resume spartalizumab treatment at the same dose and schedule. If symptoms persist or recur consider skin biopsy. 	Continue spartalizumab treatment AE resolution to ≤1 or baseline must occur within a period of 12 weeks since Grade 2 event has been identified, otherwise spartalizumab must be permanently discontinued.

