Table 8-6 Mandatory dose modification requirements and recommended clinical management guidelines for "other" potential immune-related AEs of special interest

Grade	Recommended Adverse Event management guidelines	Mandatory Dose Modification requirements					
Mild (Grade 1)	Provide symptomatic treatment	Continue spartalizumab					
Moderate (Grade 2)	 Consider interruption of spartalizumab until recovery to ≤ Grade 1 or baseline. 						
	Ensure adequate evaluation to confirm etiology or exclude other causes						
	Provide symptomatic treatment						
	Systemic corticosteroids may be indicated						
	Consider biopsy for confirmation of diagnosis						
	A specialist should be consulted						
Severe (Grade 3)	 Initiate systemic corticosteroids (prednisone or equivalent) at a dose of 1-2 mg/kg QD and other therapies as appropriate Monitor closely and consult with a specialist 	 1st occurrence: Interrupt spartalizumab until recovery to ≤ Grade 1 or baseline May restart spartalizumab treatment at the same dos and schedule 					
		AE resolution to ≤ Grade 1 or baseline must occur within a maximum period of 12 weeks sind					

Protocol/Version No.: 5, Date December 15, 2022

Other(e.g. Autoimmune neuropathy, Demyelinating polyneuropathy, Guillain Barre, Myasthenia Gravis-like syndrome, Non-infectious myocarditis, pericarditis, pancreatitis, encephalitis, and Grade 3 Fatigue with rapid onset in absence of disease progression)

Grade	Recommended Adverse Event management guidelines	Mandatory Dose Modification requirements
		a Grade 3 event has been identified, otherwise spartalizumab must be permanently discontinued.
		2 nd occurrence: Permanently discontinue spartalizumab
Grade 4	Refer to management of severe AEs	Permanently discontinue spartalizumab
Encephalitis (any grade)	Rule out infectious or other causes of moderate to severe neurologic deterioration, and consult with specialist.	Permanently discontinue spartalizumab
	If other etiologies are ruled out, administer corticosteroids at a dose of 1 to 2 mg/kg/day prednisone equivalents.	
Myocarditis or cardiac event grade>=3	Initiate systemic corticosteroids (prednisone or equivalent) at a dose of 1-2 mg/kg QD, and consult with specialist.	Permanently discontinue spartalizumab

Table 8-7 Mandatory dose modification requirements and recommended clinical management guidelines for infusion reaction events and cytokine release syndrome

Infusion reaction (NCI-CTCAE	E v4.03)	

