other clinical sequelae (e.g., renal impairment, pulmonary infiltrates) Grade 4: Life-threatening; pressor or ventilatory support indicated	 Acetaminophen Narcotics Oxygen Pressors Corticosteroids Epinephrine Increase monitoring of vital signs as medically indicated until the patient is deemed medically stable in the opinion of the investigator. Hospitalization may be indicated. 	

2nd occurrence of grade 2 irAE (including colitis/diarrhea, LFT abnormalities, rash, nephritis and other AEs as listed in table 8-6) or for grade 2 irAE lasting more than 12 weeks. Permanently discontinue spartalizumab.

6.3.2.1.2 Guidance for corticosteroids tapering for management of immune-related AEs:

Steroids should be tapered slowly and based on response/recovery of clinical symptoms. Consider to complete tapering over a period of at least 4 weeks. Slower tapering of corticosteroids therapy may be recommended if the adverse event is not showing improvement.

Protocol/Version No.: 5, Date December 15, 2022

Once corticosteroid tapering is achieved at a level of 10 mg of prednisone/day (or equivalent), spartalizumab can be restarted as indicated in the dose modification tables.

6.3.2.2 Dose modification requirements for adverse events suspected to be related to study treatment

The required dose modification and management of adverse events that are considered to be related to study medication and do not have specific management requirements noted elsewhere in the protocol are provided in Table 8-8 & Table 8-9.

Table 8-8 Mandatory dose modification requirements and recommended clinical management guidelines for hematologic adverse events suspected to study treatment

Hematologic su	spected AEs (NCI-CTCAE v4.03)	
Grade	Recommended Adverse Event management guidelines	Mandatory Dose Modification requirements
Neutropenia		
Grades 1, 2	NA	Continue spartalizumab and siltuximab

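### The text after Table 8-7 stops spartalizumab at a second Grade 2 irAE, but the mandatory liver, rash and nephritis rows set no such limit, so DLT status depends on which instruction is applied

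*Combined protocol and SAP*

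**What the plan says.** Section 6.3.2.1.1 sends the reader to event-specific tables for irAE dose modification and fixes their status: "The dosing modification requirements are mandatory, however, the AE management guidelines are recommendations". For Grade 2 events, the mandatory cells that can be read are:

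- Table 8-1 (liver tests): interrupt until recovery, then "Once recovered restart spartalizumab treatment at the same dose and schedule".
- Table 8-2 (rash): continue. The only stop is for slow resolution, which "must occur within a period of 12 weeks since Grade 2 event has been identified, otherwise spartalizumab must be permanently discontinued".
- Table 8-3 (nephritis): interrupt until creatinine recovers, then restart unchanged, with the same 12-week limit.

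After Table 8-7, which covers infusion reactions and cytokine release, comes a rule that cuts across these tables. Its first trigger is the "2nd occurrence of grade 2 irAE (including colitis/diarrhea, LFT abnormalities, rash, nephritis and other AEs as listed in table 8-6"). A second trigger, and the action for both, come next in the same text: "or for grade 2 irAE lasting more than 12 weeks. Permanently discontinue spartalizumab".

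The general list of reasons to stop spartalizumab in Section 6.3.2 mentions recurrence only for severe or Grade 3 reactions. In Section 6.2.3, Table 7 includes among the DLT criteria "Any AE that leads to permanent discontinuation of siltuximab or spartalizumab".

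**The concern.** A site managing a second Grade 2 rash, liver or nephritis event would naturally open the table for that event. It finds an instruction to continue or restart and nothing about a second occurrence. The rule that ends treatment comes after a table on a different subject. Section 6.3.2.1.2, which follows directly, sends the reader back to the dose-modification tables for restarting.

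Two things are at stake. The first is exposure: one patient stays on spartalizumab under the row and comes off under the later text. Section 6.3.2 then generally stops siltuximab too, with exceptions for objective benefit and for controlling irAEs. The second is the primary endpoint. Table 7 turns a permanent discontinuation into a DLT, so the same clinical course can be counted or not. Table 7 itself names a second Grade 2 episode only for pneumonitis, so it does not settle the question for the other events.

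**Working it through.** **Text comparison.**

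1. The later text names five event groups: colitis/diarrhea, liver tests, rash, nephritis and the Table 8-6 events.
2. For liver tests, rash and nephritis, the Grade 2 mandatory cell is readable, orders restart or continuation, and is not limited to a first occurrence.
3. For the Table 8-6 events, the only readable Grade 2 dosing text is "Consider interruption of spartalizumab until recovery to ≤ Grade 1 or baseline", and no mandatory Grade 2 entry is visible. In Table 8.0 the Grade 2 mandatory entry breaks off in the text as extracted. No conflict can be shown for either table.
4. Elsewhere the tables do separate first from second occurrence: the Grade 2 row for pneumonitis (Table 8-4) and the Grade 3 rows of Tables 8.0, 8-2, 8-3 and 8-6.
5. The later text does not say whether a second occurrence means the same irAE again or any further irAE. One Grade 2 rash followed by one Grade 2 liver event is therefore undetermined.
6. The 12-week half of the later text agrees with the rash and nephritis rows. It also falls outside the 6-week DLT window, so only the second-occurrence half matters for DLTs.

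**Effect on a cohort.** Under Section 6.2.2, one reclassified patient turns 0/3 into 1/3, so the cohort expands, or turns 1/6 into 2/6, so the MTD is exceeded.

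**Illustrative size.** The plan states no DLT rate and no rate of recurrent Grade 2 irAEs, so there is no figure of its own to reproduce. Both inputs are assumptions:

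- p = background DLT risk without the second-occurrence rule.
- q = share of the other patients who become DLTs when the rule is applied.
- Combined risk: p' = p + (1 − p)q.
- A level clears 3+3 with 0/3, or with 1/3 followed by 0/3: P(clear) = (1 − p')^3 + 3p'(1 − p')^5.
- P(too toxic) = 1 − P(clear).

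For p = 0.20:

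- q = 0: p' = 0.200; P(clear) = 0.709; P(too toxic) = 0.291.
- q = 0.02: p' = 0.20 + 0.80 × 0.02 = 0.216; P(clear) = 0.674; P(too toxic) = 0.326.
- q = 0.05: p' = 0.20 + 0.80 × 0.05 = 0.240; P(clear) = 0.622; P(too toxic) = 0.378.
- q = 0.10: p' = 0.20 + 0.80 × 0.10 = 0.280; P(clear) = 0.536; P(too toxic) = 0.464.

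For p = 0.10 and the same four values of q, P(too toxic) is 0.094, 0.125, 0.176 and 0.270.

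**The case against.** The best defence is that the passages can all be followed. No readable Grade 2 row for liver tests, rash or nephritis says what to do at a second Grade 2 event, and the later text supplies that rule in the same section. It leaves out pneumonitis and endocrinopathy, which have recurrence rules of their own, so it looks like a deliberate gap-filler. Read that way, the patient discontinues and Table 7 makes the event a DLT. This stands, and it is why a reader who infers a flat contradiction goes too far.

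Two other inferences also fail. One is that every named event has a mandatory row ordering continuation or restart; this is shown for three of the five groups only. The other is that the rash table overrides the stop because it says "If symptoms persist or recur consider skin biopsy". That sentence is in the management column, which is advisory.

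The layout is uncertain as well. The later text may be a closing table row flattened in extraction, so little should rest on its appearance.

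Finally, Section 6.2.3 requires review of Grade 2 and higher events before a higher level opens, and Section 11.0 requires DSMC approval of escalation. That review could catch inconsistent handling. However, neither section says which instruction governs, and review at escalation comes after the site has already continued or stopped the drug.

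The gap-filler reading is reasonable but not secured. The tables are named as the mandatory source, they state a second-occurrence rule in other rows, and the general list in Section 6.3.2 does not carry this one.

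**Conclusion.** The point holds as an unreconciled pair of instructions for Grade 2 liver, rash and nephritis irAEs. A related second event of these kinds within 6 weeks is a DLT if the text after Table 8-7 is applied, and not one on that ground if only the row is applied. A single such patient can change a 3+3 decision.

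How often this would happen cannot be taken from the documents. At an assumed 20% background risk, the chance of declaring a level too toxic rises from 29% to 33%, 38% or 46% as 2, 5 or 10% of the other patients are reclassified. These figures show direction and sensitivity and are not a forecast.

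A reader might take the 28% rash rate with siltuximab (15/53, Section 4.1.2.1, Table 3) as evidence for the upper end. It does not serve: it is any-grade rash over the first 8 infusions in Castleman's disease, with 12% on placebo, and says nothing about repeated immune-related Grade 2 episodes within 6 weeks.

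**What to change.** Reconcile the text after Table 8-7 with the general list in Section 6.3.2 and with the Grade 2 rows of Tables 8-1, 8-2, 8-3 and 8-6, and check that Table 8.0 agrees. Write whichever rule the sponsor chooses into the mandatory Grade 2 cell of each table, so that a site using one table sees the whole instruction. State whether a second occurrence means the same irAE or any irAE. Confirm in Table 7 whether the discontinuation criterion is meant to capture a stop triggered by recurrent Grade 2 events. Which clinical rule applies is for the sponsor to decide, and none is proposed here.

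The cost is a wording amendment to the dose-modification tables and one clarifying line in Table 7. It needs no extra patients, visits or procedures.

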6.3.2 Dose modification and dose interruption for spartalizumab and siltuximab

General dose modification instructions:

Siltuximab and spartalizumab have class-specific safety profiles based on their mechanism of action but may also cause AEs that overlap. For management of AEs which can be clearly attributed to siltuximab or spartalizumab, independent dose modification for either agent is allowed. For AEs without clear attribution to either study treatment, management of toxicity should include dose modifications of both agents.

Overall AEs are to be graded according to NCI-CTCAE v4.03 (http://ctep.cancer.gov). All dose interruptions and the reason for the dose interruption must be documented in the eCRF.

Overall, patients with AEs suspected to be related to *spartalizumab* including those of potential immune-mediated etiology (irAE) may need to interrupt or permanently discontinue spartalizumab as outlined in Section 6.3.2. In general, study treatment with spartalizumab must be permanently discontinued in case of:

- Any life-threatening adverse reactions (excluding endocrinopathies controlled with hormone replacement therapy)
- Persistent Grade 2 or 3 adverse reactions (excluding endocrinopathies controlled with hormone replacement therapy) that do not recover to <= Grade 1 within 12 weeks after last dose of study treatment
- Inability to reduce the dose of steroids (for the management of irAE) to 10 mg/day or less of prednisone or equivalent (or as indicated in the tables below) within 12 weeks
- Any severe or Grade 3 recurring treatment-related adverse reaction

The 12 weeks' timeframe will begin from the time the irAE reaches a grade that leads to spartalizumab interruption.

Overall, patients with AEs suspected to be related to *siltuximab* include pruritus, increased weight (edema), rash, hyperuricemia, neutropenia, and upper respiratory tract infection. Rare side effects include gastrointestinal perforation. Toxicities may require interruption of therapy,

Protocol/Version No.: 5, Date December 15, 2022

dose reduction or permanent discontinuation from trial as detailed in section 6.3 and Tables 8-8 and 8-9. In general study treatment with siltuximab must be discontinued for:

- Gastrointestinal perforation
- Grade 4 weight gain
- Grade 4 upper respiratory tract infection
- Recurrent or severe grade 3 treatment-related adverse events.
- Life threatening adverse events
- Interruption of therapy for longer than 12 weeks

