Patients should be instructed to return to the study site as soon as possible (instead of waiting for their next scheduled visit) if they experience symptoms consistent with an irAE. Patients who experience a new or worsening irAE should be contacted and/or evaluated by the study site more frequently.

Based on experience from compounds with similar mechanism of action of spartalizumab and published guidelines (Haanen, 2017), instructions have been developed regarding how to identify, assess severity and manage irAEs that may occur in patients receiving spartalizumab. Dose modification requirements and AE management guidelines for the potential irAEs are provided in the following tables: diarrhea/colitis (Table 8-0), hepatitis (liver laboratory alterations) (Table 8-1), skin (rash) (Table 8-2), nephritis (Table 8-3), pneumonitis (Table 8-4), endocrinopathies (Table 8-5), and other potential immune-related AEs (Table 8-6). Any Grade 4 irAE must result in permanent discontinuation of spartalizumab. In addition, guidance for management of spartalizumab -infusion reaction & cytokine release syndrome is provided in (Table 8-7).

Under the category of OTHERS (Table 8-9) are included several irAE of interest that must be managed specifically and for which no specific guidance are provided in the table below. OTHERS include (but is not restricted to) the following events: Autoimmune neuropathy, demyelinating polyneuropathy, Guillain-Barre, myasthenia Gravis-like syndrome, non-infectious myocarditis, non-infectious pericarditis, pancreatitis, encephalitis, and, rapid onset of Grade 3 fatigue in the absence of disease progression.

Protocol/Version No.: 5, Date December 15, 2022

Patients receiving spartalizumab, may experience other irAEs than those listed in this document, therefore, all AEs of unknown etiology associated with drug exposure should be evaluated to determine if it is possibly immune-related. In cases where the specific irAE is not listed in the tables below, the investigator should follow the dose modification requirements in section 6.3.2 which details the measures to be taken for suspected (could be potentially immune-related or non-immune-related) AEs. Investigators are encouraged to contact the Sponsor as needed to discuss cases that warrant separate discussion outside of the scope of the current instructions.

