Symptomatic endocrinopathy (e.g., hypophysitis, adrenal insufficiency, hypothyroidism, hyperthyroidism)	 Consider Endocrinology consultation Rule out infection/sepsis and other alternative causes with appropriate cultures and imaging Treat with an initial dose of methylprednisolone 1 to 2 mg/kg intravenously followed by oral prednisone 1 to 2 mg/kg per day. (only for lifethreatening endocrinopathies) Replacement of appropriate hormones may be required as the steroid dose is tapered Hypophysitis with clinically significant adrenal insufficiency and hypotension, dehydration, and electrolyte abnormalities (such as hyponatremia and hyperkalemia) constitutes adrenal crisis Consider hospitalization and intravenous methylprednisolone should be initiated. 	Interrupt spartalizumab until recovery to mild or no symptoms, and controlled with hormone replacement therapy Once recovered or controlled with hormone replacement, restart spartalizumab at the same dose and schedule Hypothyroidism may be managed with replacement therapy without treatment interruption (unless lifethreatening) Permanently discontinue spartalizumab for lifethreatening endocrinopathies (i.e. hyperthyroidism, adrenal insufficiency, hypophysitis) or recurring severe/lifethreatening events not controlled by hormone replacement therapy.
Autoimmune diabetes (Grade 3 or symptomatic hyperglycemia)	Initiated: Initiate anti-glycemic therapy (i.e. insulin) as medically indicated and monitor glucose levels regularly until metabolic control is achieved	Interrupt spartalizumab until recovery to grade 1 or baseline Once recovered, restart spartalizumab treatment at the same dose and schedule
Autoimmune diabetes (Grade 4 hyperglycemia or life- threatening complications)	Same as Grade 3	 Second occurrence: permanently discontinue Permanently discontinue spartalizumab

Management for immune-related:

Protocol/Version No.: 5, Date December 15, 2022

a. For non-life-threatening immune-related endocrinopathy, the administration of corticosteroids can be omitted, and the patient can be treated with physiologic replacement of the deficient hormone (e.g. provide levothyroxine for immune-related hypothyroidism, and omit administration of corticosteroids).

b. Use corticosteroids only used if endocrinopathy is life-threatening or as physiologic replacement for primary or secondary adrenal insufficiency.

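### The grade 2 stopping line below Table 8-7 omits the exemption for hormone-controlled endocrinopathies that Section 6.3.2 gives and Table 8-5 reflects

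*Combined protocol and SAP*

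**What the plan says.** Three places in the protocol govern a persistent grade 2 endocrine event.

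- **Section 6.3.2, general rule.** Spartalizumab stops permanently for "Persistent Grade 2 or 3 adverse reactions (excluding endocrinopathies controlled with hormone replacement therapy) that do not recover" to grade 1 or lower within 12 weeks. The bullet on life-threatening reactions carries the same exception. The section adds that the 12-week "timeframe will begin from the time the irAE reaches a grade that leads to spartalizumab interruption".
- **Table 8-5, symptomatic endocrinopathy.** The first instruction is "Interrupt spartalizumab until recovery to mild or no symptoms, and controlled with hormone replacement therapy"; the next is "Once recovered or controlled with hormone replacement, restart spartalizumab at the same dose and schedule". The table also says "Hypothyroidism may be managed with replacement therapy without treatment interruption", unless the event is life-threatening. Permanent stopping in this row is kept for life-threatening events, or recurring severe or life-threatening events that replacement does not control.
- **The line below Table 8-7.** It requires a permanent stop for a second grade 2 immune-related event, with a bracketed list of examples, "or for grade 2 irAE lasting more than 12 weeks. Permanently discontinue spartalizumab". It has no endocrine exception and does not say when the 12 weeks begin.

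The text before Table 8.0 makes the dose-modification requirements mandatory and the management advice optional. Section 6.3.2.1.1 counts endocrinopathies among the immune-related events and notes that some need life-long replacement.

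**The concern.** Endocrinopathies are the immune-related events for which the protocol itself foresees life-long treatment, so they are obvious candidates to outlast 12 weeks while clinically controlled. For them, one mandatory rule says stop permanently and two others say continue or restart. No text says which prevails.

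The cost to a patient can exceed the loss of one drug. Section 6.3.2 says that when either agent is permanently stopped, the other should be stopped too. The exceptions are single-agent continuation after discussion in a patient with CR, PR or SD, and siltuximab used to control immune-related events. A patient stopped under this line therefore loses the combination and may lose all study treatment. In the analysis, combination exposure would be shortened and the Section 12.5.1.1 summary of adverse events leading to discontinuation would gain events that the other rules would not have produced.

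**Working it through.** No arithmetic beyond comparing time windows applies; the check is to run the same patient through each rule.

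| Patient | Section 6.3.2 | Table 8-5 | Line below Table 8-7 |
|---|---|---|---|
| A. Hypothyroidism on replacement, never interrupted, still graded 2 after 12 weeks | Exempt; its clock never starts | Continue | Stop, if the duration runs from onset |
| B. Symptomatic event, interrupted, then restarted as controlled, still graded 2 after 12 weeks | Exempt | Restart, same dose | Stop |
| C. Second grade 2 thyroid, adrenal or pituitary event, controlled on replacement | No recurrence stop at grade 2 (its recurrence bullet concerns severe or grade 3 reactions) | Not stopped | Stop, if the list is non-exhaustive |
| D. Controlled and graded 1 or lower | Not triggered | Continue | Duration rule not triggered |

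**Does the bracketed list limit the line?** It names colitis/diarrhea, liver tests, rash, nephritis and Table 8-6 events, but not endocrinopathies. It opens with a word of inclusion and is attached to the second-occurrence part. The duration part has its own unqualified subject. The list therefore does not clearly take endocrinopathies out of either part.

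**Can disease be controlled and still above grade 1?** The documents do not grade controlled disease, and the thyroid, adrenal and pituitary rows of Table 8-5 are sorted by symptoms. But the Section 6.3.2 exception applies to a rule triggered only by failure to reach grade 1 or lower. If control always meant grade 1 or lower, the exception would be empty. It covers grades 2 and 3 together, so it shows that the authors foresaw controlled disease above grade 1, not how often it sits at grade 2.

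**How wide is case B?** Narrow. The first Table 8-5 instruction asks for mild or no symptoms as well as control, and Table 8-6 equates mild with grade 1. The second instruction accepts control as an alternative to recovery, which leaves the case open.

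**Is the exemption the intended policy?** Probably. Section 6.3.2 states it twice, and exclusion criterion 5 admits patients with residual autoimmune hypothyroidism needing only replacement.

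**Does the duration rule touch dose finding?** The DLT window is 6 weeks and the expansion stopping rule looks at the first 8 weeks. Since 12 > 8 > 6, a stop for an event on treatment lasting more than 12 weeks falls outside both.

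**The case against.** The best reply is that the rules can be harmonised. Section 6.3.2 states the same 12-week grade 2 rule with the exception, and Section 6.3.2.1.1 assigns "endocrinopathies (Table 8-5), and other potential immune-related AEs (Table 8-6"), so a sensible site would read a short summary line under the infusion-reaction table subject to both. The line may have been meant only to fill gaps in other tables: its list leaves out pneumonitis and endocrinopathies, and each has its own scheme. On the Section 6.3.2 clock, case A never arises. Investigators are also encouraged to raise unclear cases with the sponsor.

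This is a plausible account of intent, and it is a reason to expect few wrong stops. It does not remove the conflict: the clock is not carried into the line, the list does not govern the duration part, no order of precedence is given, and the requirements are mandatory.

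One part of the reply stands in full. A reader might infer the exemption from the lack of a 12-week limit in Table 8-5, since the grade 2 rash row prints one ("within a period of 12 weeks since Grade 2 event has been identified") and the nephritis and pneumonitis rows do too. That inference is unsafe. The grade 2 liver row of Table 8-1 and the moderate row of Table 8-6 also print no limit. The point rests on the stated exception in Section 6.3.2 and the restart and continuation instructions in Table 8-5.

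**Conclusion.** Wrong as written, minor. The line omits an exception that the same section states for the same 12-week rule, and its second-occurrence part has the same gap if the list is non-exhaustive.

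Few patients are likely to be affected, possibly none. The conflict over duration needs an endocrinopathy that is controlled on replacement, still graded 2 after 12 weeks, in a patient still on treatment. The documents give no incidence and no grading of controlled disease, so any count would rest on outside assumptions and none is given. If controlled disease is always graded 1 or lower, the duration part is merely unclear.

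A reader might infer three stronger things; the documents support none of them.

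- **Added toxicity.** The error runs the other way: it stops treatment too readily.
- **Distorted dose finding.** Table 7 does count an adverse event leading to permanent discontinuation as a DLT. But the duration rule cannot act within 6 or 8 weeks. The second-occurrence part would need two separate grade 2 endocrine events in one patient inside those windows, which nothing in the documents suggests. The DLT assessment, the RP2D and the expansion stopping rule are treated as unaffected.
- **Lost efficacy data.** Sections 6.7 and 6.7.4 continue tumor assessment after a stop for reasons other than progression, so response and progression are still collected.

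**What to change.** Rewrite the line as one sentence and apply the Section 6.3.2 exception to both parts. It should require permanent discontinuation of spartalizumab for a second occurrence of a grade 2 immune-related event (keeping the existing list) or for one lasting more than 12 weeks, and end with a clause such as: *in both cases excluding endocrinopathies controlled with hormone replacement therapy, which follow Table 8-5*.

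Amending only the duration part would leave case C open. Pointing to Table 8-5 also keeps that table's own stopping rules in force, including those for life-threatening endocrine events and autoimmune diabetes.

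The cost is one clause in the next protocol amendment, with no new data, visits or patients.
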